#### 8.2.3. Timing of PK blood samples and ECGs

A pre-bedaquiline dose blood sample must be taken within 1 hour of the next scheduled bedaquiline dose. A pre-ART blood sample should also be taken at this time in HIV co-infected patients on lopinavir/ritonavir and nevirapine.

A 12-lead ECG, which is in addition to the 12-lead ECG performed at each study visit as per the Stage 2 assessment schedule (Table 6) above), must be done 4 hours after the bedaquiline dose. A post-bedaquiline dose blood sample must then be taken 4-5 hours after bedaquiline intake and within 20 minutes of the post-dose ECG. The schedule for collection of PK blood samples and post-dose ECGs is outlined in Table 7 below.

**Table 7: PK Sample Collection Timings** 

Visit	Pre- bedaquiline dose PK blood sample	Pre-ART dose blood sample	Post- bedaquiline dose PK blood sample	Additional post-bedaquiline dose 12-lead ECG
Randomisation	V	V		
2	√	V	√	√
4	V			
12	V	V	√	√
24	V		√	√
40	√		√ (Arm C only)	√ (Arm C only)
76	√			
120¹	√			
132¹	√			

<sup>1 PK samples will not be taken after the projected Week 96 visit of the last patient randomised i.e. approximately end of November 2021.

## 8.2.4 Additional PK investigations for toxicity or change of ART

An additional blood sample should be collected at any visit when BDQ is withheld for suspected toxicity. If the antiretroviral treatment regimen of a patient is changed during the 40-week treatment period for Regimen C or the 28-week treatment period for Regimen D, a pre-dose sample should be collected, followed by collections as described above.

The exact date and time of each PK blood sample and the respective previous 2 doses of bedaquiline will be recorded in the CRF. For participants receiving lopinavir/ritonavir or nevirapine, the last three doses and dates of the ART prior to each PK sample time-point will be recorded in the CRF.

#### 8.2.5 Bioanalysis

The bioanalysis will be performed by a contract research organization (CRO), under the supervision of the Sponsor and/or Janssen. Samples will be analysed using a validated and sensitive liquid chromatography-mass spectrometry/mass spectrometry method

# 8.3 Procedures for assessing safety

Throughout this study, patients will be closely monitored for signs and symptoms of drug toxicity. All toxicities leading to the study therapy being temporarily or permanently discontinued and all Grade 3 or greater toxicity effects will require thorough investigation with relevant clinical and laboratory tests, as clinically indicated.

These should be repeated as needed until final resolution or stabilisation of the toxicity; if this is after the end of the trial, follow-up will be the responsibility of the treating clinician. All symptoms and laboratory findings will be graded according to severity using DAIDS criteria. Laboratory events will be reported as adverse events only if clinically significant. If the patient has a medical diagnosis at randomisation whose signs or symptoms worsen during the study to a Grade 3 or greater, this is a notable event (NE) that must be reported. Other notable events and SAEs will be reported as they occur to the MRC CTU, as well as to other bodies required to be notified in each country. For details of safety reporting see Section 13.

### 8.3.1 ECG Monitoring

Several of the drugs used in the STREAM regimens have the potential to prolong QT, therefore ECG monitoring is used in both Stage 1 and Stage 2 to identify and manage patients who are at risk.

In Stage 1, all patients will have a 12-lead ECG immediately prior to randomisation and will be ineligible if the QT or QTcF interval is more than or equal to 500ms. An ECG will be recorded 4 hours after the first dose of trial treatment. Further ECGs will be performed weekly for the first four weeks, and then every four weeks until 52 weeks after randomisation. If a patient has a QT or QTcF of 450ms or more, then a second ECG should be conducted at least 10 minutes after the first ECG.

In Stage 2, if there is a QT or QTcF measurement of 450 ms or more the patient will not be eligible for randomisation. ECG monitoring for Stage 2 involves 12-lead ECGs undertaken at baseline (pre and 4 hours post-dose at the randomisation visit), weekly for the first four weeks and at every visit until week 76. All patients whose QTcF at week 76 is higher than their baseline recordings will continue to have 12-lead ECG monitoring at every visit until the confirmed QTcF is either less than 10 ms above the baseline value or below 450 ms.

In addition, patients in arms C and D enrolled at sites that have been pre-selected for the PK substudy, should also have an ECG 4 hours after administering treatment at the week 2, 12, 24and 40 visits (see Section 8.2.3).

Any QT or QTcF prolongation to more than or equal to 500 ms while on treatment is considered a notable event and should be reported immediately to MRC CTU (See Section 13).

Patients found to have a QT or QTcF more than or equal to 500 ms on a 12-lead ECG at any point during treatment will be further investigated. The ECG should be repeated and if confirmed, the investigator should attempt to identify the cause, including checking and correcting abnormal  $K^+$ ,

Ca+2, and Mg+2. If the patient is taking any drugs suspected of causing QT prolongation they should be withheld and the tests repeated to try to identify the cause. Further details are provided in the STREAM Patient Management Guide.

#### 8.4 Post-treatment schedule

After completion of treatment the patient will be reminded of the need for follow-up visits by the Principal Investigator, or recruiting clinician, and be informed of the date of their next visit.

During the follow-up visits, the following procedures will be undertaken:

- Clinical investigations (as outlined above) will be carried out
- Patients will be asked about any adverse events that may have occurred after their last visit and any concomitant medications they may have received.

There may be times when the PI requests additional tests for a patient depending on their disease progression at a particular visit.

# 8.5 Changes to treatment or follow-up

## 8.5.1 Interruptions to treatment

The treatment regimens or selected drugs may be interrupted at the discretion of the local PI or treating clinician:

- For a serious adverse event
- For a QT or QTcF measurement of more than or equal to 500ms
- If ALT/AST rise to more than or equal to 5 times ULN, or if AST/ALT rise to more than or equal to 3 times ULN in the presence of a total bilirubin rise to more than or equal to 2 times ULN
- If the investigator decides to withhold treatment in the interest of the safety and well-being of the participant.

If treatment is interrupted for a suspected serious drug reaction, attempts should be made to identify the drug concerned. Further guidance on expected toxicities is provided in the STREAM Patient Management Guide. After resolution of the suspected adverse reaction, treatment may be gradually re-introduced until the allocated regimen has been re-instituted.

If treatment with one of the core drugs other than bedaquiline (i.e. kanamycin or amikacin, isoniazid, moxifloxacin or levofloxacin, and clofazimine) is missed in either the intensive or continuation phase of one of the study regimens this can be made up by extending this phase of the regimen by the number of treatment days missed at the discretion of the treating physician and in the absence of ongoing toxicity.

Bedaquiline treatment interruptions will be handled separately to those involving the other core drugs, and are managed based on the phase of bedaquiline dosing:

- Treatment interruptions during the 14-day loading period:
  - All treatment interruptions during the loading phase of bedaquiline must be reported to the clinical team at the MRC CTU within one working day of the site becoming aware, and advice will be given on a case by case basis

- For interruptions of less than or equal to 14 days, bedaquiline loading should resume at the point of the last dose to complete the total doses required in the loading period with the doses previously received taken into account
- For interruptions of >14 days, treatment should be re-started at the beginning of the loading period. The full 14 days of loading should be completed with no accounting for doses taken already
- Only one treatment interruption is allowed during the loading phase and restarting treatment is not permitted after interruptions of >30 days
- Treatment interruptions during the thrice-weekly maintenance dosing period:
  - Bedaquiline can be resumed at maintenance dosing for interruptions of up to 30 days
  - More than one interruption of up to 14 days is allowed but only one interruption of between 15 and 30 days is permitted
  - Restarting bedaquiline after treatment interruptions of >30 days is not permitted
- A maximum of 40 weeks' of bedaquiline (measured by number of doses, not by time since first dose) can be administered to any patient

There is no requirement to change the dates of scheduled PK sampling visits in response to treatment extensions. Treatment adherence must be accurately recorded, and this data can be used to adjust calculated pharmacokinetics.

In the event that the local PI considers that treatment needs to be modified or changed, he or she should inform MRC CTU by submission of an SAE/NE form and discuss treatment plans with a member of the central clinical team.

#### 8.5.2 Missed visits

For each patient, clinic staff will obtain or confirm contact information. In the event that a patient misses a scheduled appointment, a Home Visitor will try within the week following the missed appointment to establish communication with the patient and/or treatment supervisor through all possible means which they have approved and while protecting their confidentiality (e.g. by telephone if this is possible, writing to the patient and contacts, and/or visiting the patient's home or workplace). All attempts to locate a patient following each missed appointment should be documented in their records. The need to attend all scheduled follow-up visits will be emphasised to all study patients at every visit.

#### 8.5.3 Visit after a missed appointment

Patients who miss their scheduled appointment will be contacted and arrangements made for a new appointment. If patients are not successfully reached by phone/text messaging, a home visit should be made and the outcome recorded on a home visit form.

Patients returning after missed appointments should undergo the scheduled assessments for the visit that is closest to the time from randomisation (e.g. if a patient returns to the clinic at or near to Week 16 after missing their visits for weeks 8 and 12, the visit for that day should be recorded as Week 16 and the Week 16 assessments undertaken). Subsequent visits will continue as scheduled. However, treatment to be prescribed should be determined by the actual number of days on which a patient has taken their medication and not by the length of time they have been in the study.

### 8.5.4 Loss to follow-up

If a patient does not return to the clinic before the study is closed, a Final Form will be completed at the time of study closeout, after reasonable effort to contact the patient has been made. The form should indicate that the patient was lost to follow-up. The "loss to follow-up" designation cannot be made for any patient until after the patient's scheduled Week 132 visit.

## 8.5.5 Follow-up of patients discontinued from treatment

Every effort should be made to follow up all patients for the full duration of the study, including those whose treatment is discontinued or whose treatment is changed. A reduced frequency of follow up may be appropriate, and if necessary, should be agreed with the MRC CTU. In this event, a final status form should be completed. For patients who have discontinued follow-up visits, but have not withdrawn consent, the vital status should be obtained at least every six months until Week 132, if necessary by telephone follow up.

If a patient can be contacted and declines further study participation, an investigation into their reasons will be conducted, and the reasons documented. An attempt will be made to have him/her come to the clinic for a final visit, or at least obtain a sputum sample for the assessment of the primary efficacy outcome.

#### 8.6 Trial closure

The trial will be considered closed when the last patient has completed their final visit and all followup and laboratory reports have been received.

The trial may be terminated early by the Trial Steering Committee (TSC), on the advice of the Independent Data Monitoring Committee (IDMC) (see sections 19.2 and 19.3). In addition, MRC CTU and the Sponsor have the right to close this trial and/or a site, at any time, although this should occur only after consultation between involved parties and with the agreement of the TSC.

At trial closure, the local and central Research Ethics Committees/Institutional Review Boards and the regulatory authorities that approved the trial should be informed. It is the responsibility of the sponsor to inform the main REC within 90 days of the 'end of the trial' that the trial has closed.

Following trial closure remaining samples will be transferred to a biobank following approval from the TSC.

Should a site be closed prematurely, trial materials will be disposed of according to the site agreement with the Sponsor or MRC CTU. The Principal Investigator will retain all specified documents, for at least 15 (fifteen) years, until notification is given by MRC CTU for destruction. Patients currently on treatment will be transferred to another STREAM site where available, or referred to the National Tuberculosis Programme for completion of treatment and further management.

# 8.7 Bacteriology

The following bacteriological tests will be performed at the site microbiology laboratory: smear, culture, diagnostic line probe assays or GeneXpert. At each visit, except for Week 1, Week 2, and Week 3, sputum samples will be collected. At most visits during Stage 1 this will be a single specimen unless otherwise indicated in sections 8.1.1, and will be two specimens during Stage 2. All specimens will be tested for AFB smear and culture. Because early morning samples are preferred, at the conclusion of each visit patients should be given a sputum container for sample collection to be presented at their next visit. The second sample will be taken as a spot sample at the time of clinic attendance. When two samples are required, if the patient does not bring an early morning sample, two spot samples will be collected at the visit. If a patient is unable to produce sputum this should be documented on the CRF.

The selected methods and techniques for use by the sites may not be the most sensitive ones, but they are simple and applicable at any site with high reproducibility, thus allowing a high degree of standardisation. Long-term follow-up will compensate for imperfect sensitivity. These methods are:

- hot Ziehl-Neelsen (ZN) or auramine fluorescence technique for all study smears
- FDA vital staining for selected smears in some sites (see 5.2.1)
- decontamination without neutralisation centrifugation and direct inoculation on acidified Ogawa (Kudoh medium) for isolation of mycobacteria and subsequent identification of all positive study cultures using any locally available method (e.g. GeneXpert, Hain Genotype MTBDRplus, SD Bioline).
- Hain Genotype MTBDRPlus line probe assay (LPA) from smear-positive sputum or GeneXpert System (Cepheid automated diagnostic test to identify rifampicin resistant Mycobacterium tuberculosis) for screening of suspects. If one of these tests or other DST shows at least resistance to rifampicin, the Hain Genotype MTBDRsl LPA will be performed to exclude fluoroquinolone and second-line injectable resistance.

To increase the probability of having at least one good baseline isolate, the sites should also inoculate the remaining part of the randomization and screening samples using their preferred culture method and medium (e.g. MGIT after neutralization and centrifugation).

All positive isolates, except those of week 4, will be sent to the designated study reference laboratory, to confirm species identification and susceptibility status. This includes diagnostic strains and recurrence strains, in case of failure or relapse besides isolated positive cultures in-between successive negatives. Strains from recurrences will be tested for DST as well as fingerprinting, to confirm their identity and to compare their resistance pattern with the originally isolated strain. The reference laboratory will store all study strains at -80°C and local laboratories will store at -20°C.

The techniques to be used at the reference laboratory are:

- Slow phenotypic DST using the proportion method on Löwenstein-Jensen medium for first line drugs and agar-based Middlebrook 7H11 medium for second line drugs; for difficult strains, the minimum inhibitory concentration (MIC) and DNA sequencing can be used to arrive at the most correct result
- Fingerprinting; MIRU-VNTR analysis (mycobacterial interspersed repetitive units—variable number of tandem repeats).

A detailed description of the various laboratory tests is found in the STREAM Microbiology Manual.

Results of resistance tests undertaken by the reference laboratory are primarily for analysis purposes and will not be routinely provided to the sites. Treatment changes will not be suggested on the basis of these results unless a patient is not doing well and it is decided that a change of treatment is required.

However, if any patients are found to have XDR-TB (confirmed resistance to fluoroquinolones and second-line injectables from phenotypic DST) from samples collected at baseline, these results will be provided to sites, and the patients should be withdrawn from trial treatment and treated according to national guidelines.

### 8.8 Health economic assessment

In sites participating in the health economic component of STREAM, data relevant to the health economic assessments will be collected as explained below:

### 8.8.1 Health system costs

Health system costs will be obtained through:

- An analysis of health worker time involved in prescribing, monitoring, and supervising the regimens in each country, health worker salary and benefits data from the Ministry of Health and health facility records based on grade of staff rather than named individuals
- A full assessment of the health system costs of delivering the MDR-TB regimens, including tests performed, consumables used, in-patient stay costs, drugs administered and overheads
- Standard costs of supplies from hospitals' accounting records where possible. Other
  appropriate sources such as private healthcare facilities costs will be used if data not available
  in hospitals' records
- An analysis of the costs associated with the diagnosis and management of serious adverse events (SAEs) caused by MDR-TB or its treatment. This will include all tests performed, examinations, investigations, in-patient stays and medication received, as well as staff costs.
- Summing the costs of each resource used in delivering the MDR-TB regimens

Costs will be assessed as one-off costs required for establishing the regimens and as costs for recurrent costs for sustaining it.

### 8.8.2 Patient and household costs

Data on patient and household costs will be collected through patient interviews based on the STOP-TB questionnaire. Interviews will take place at intervals of 12 weeks after initiation of treatment. The interviews will include questions out-of-pocket costs on fees paid to the health system, such as drugs and laboratory test costs, transport, food and accommodation costs incurred as a result of the treatment process. In addition, there will be questions regarding quality of life as well as time lost from economic activities.

### 8.8.3 Socio-economic status

The socioeconomic status of patients will be assessed through asking patients about asset ownership. The assets will be determined based on existing poverty analyses or similar sources (demographic and Health Surveys, population income surveys or census data) for the country or region within the country. These questions about asset ownership will be included in the demographic assessment at randomisation and again every 12 weeks after the initiation of treatment.

# 9 DISCONTINUATION FROM TREATMENT

In consenting to trial participation, patients are consenting to study treatment, follow-up and data collection. If a patient wishes to discontinue their allocated study treatment they should not be withdrawn from follow-up unless they expressly request it. Patients should be told about the importance of remaining on follow-up, or failing this, of allowing routine follow-up data to be used for study purposes.

The treating clinician will be discouraged from changing or restarting treatment without evidence of treatment failure or recurrence of MDR-TB. As soon as the treating clinician has any indication of a treatment failure, recurrence, or serious toxicity, they should contact the STREAM central clinical team to discuss whether treatment should be modified. Guidelines for retreatment, in the STREAM Patient Management Guide, will be used to inform the decision, which will be made on a case-by-case basis using all the available bacteriological and clinical data. If the decision is made not to retreat, then the case should be reassessed as further data accumulates with further discussions with the STREAM central clinical team as necessary.

# 9.1 Discontinuation of allocated regimen

The Investigator must make every reasonable effort to keep each patient on their allocated regimen and in follow-up for the whole duration of the study. However, if it is necessary to discontinue or change a patient's allocated regimen, every reasonable effort will be made to ensure the patient continues to be followed-up.

The following are justifiable reasons for the Investigator to discontinue or modify a patient's allocated treatment:

- Unacceptable toxicity
- Patient refuses to take study drugs
- 3. Serious violation of the study protocol (including persistent patient attendance failure, non-adherence to treatment and persistent non-compliance)
- 4. The Investigator decides to discontinue a patient's treatment for clinical reasons not related to the regimens
- 5. Evidence of treatment failure based on consistently positive bacteriology usually accompanied by signs and symptoms of disease
- 6. Pregnancy; women who become pregnant will stop their allocated trial treatment, and be treated according to local practice
- 7. A confirmed QT or QTcF more than or equal to 500 ms on 12-lead ECG in patients for whom no other cause can be identified
- 8. Confirmed resistance to fluoroquinolones and second-line injectables from phenotypic DST.

If it is local practice to do so, results from local drug susceptibility tests showing a patient's isolate is resistant to trial medications may be used to justify a change of treatment for patients, although this is discouraged if the patient is doing well clinically. Drug susceptibility test results alone should not be used to justify a change or discontinuation of treatment for patients in the regimens, although patients found to have resistance to **both** fluoroquinolones **and** second-line injectables from phenotypic DST (confirmed XDR-TB) should be withdrawn from trial treatment and treated according

to national guidelines (see section 5.5.1). If these results are obtained from a local laboratory, a patient can remain on trial medication at the discretion of the treating clinician if the patient appears to be doing well on treatment. However, if results from the central laboratory confirm XDR-TB, then the patient should be removed from the trial and treated according to national guidelines.

Should drug unavailability occur, local supply of drug(s) through the National Tuberculosis Programme or local market will be considered (after ensuring acceptable quality) for all study drugs except bedaquiline while regular study supplies are replenished. In instances where drug(s) remain unavailable for any period of time the central clinical team will be consulted to advise on appropriate management.

Any change or discontinuation of treatment should be discussed with the STREAM central clinical team before a decision is made, unless in response to a medical emergency.

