# 5.5 Late identification of drug-resistance or drug-sensitivity

## 5.5.1 Late identification of fluoroguinolone/injectable-resistance

In sites that currently undertake phenotypic second-line drug susceptibility resistance testing (DST), results from pre-treatment samples that provide evidence of fluoroquinolone, or second-line injectable resistance may become available after randomisation. In such cases, the patient's clinical progress should be taken into account before making any changes on the basis of the results, in consultation with the central clinical team. However, if patients are found to have XDR-TB (defined as resistance to fluoroquinolones **and** second-line injectables from phenotypic DST) these patients should be withdrawn from trial treatment and treated according to national guidelines.

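### Protocol 9.1 tells sites to remove a patient with centrally confirmed XDR-TB from the trial, while 5.5.1, 8.7 and 9.1 itself stop only trial treatment and the follow-up rules keep such patients in

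*Protocol*

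**What the plan says.** Protocol 9.1 deals twice with resistance to both fluoroquinolones and second-line injectables. The first statement covers patients with this result "from phenotypic DST (confirmed XDR-TB) should be withdrawn from trial treatment and treated according" to national guidelines, and it cross-refers to 5.5.1. Two sentences on the source of the result follow. With a local-laboratory result, "a patient can remain on trial medication at the discretion of the treating clinician if the patient appears to be doing well" on treatment. With a central result the instruction changes: "if results from the central laboratory confirm XDR-TB, then the patient should be removed from the trial and treated according to national guidelines".

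Two other sections address the same finding. Section 5.5.1, on results from pre-treatment samples, says that "these patients should be withdrawn from trial treatment and treated according to national guidelines". Section 8.7 covers XDR-TB found "from samples collected at baseline, these results will be provided to sites, and the patients should be withdrawn from trial treatment".

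On follow-up, the opening of 9.1 says that if a regimen has to be stopped or changed, "every reasonable effort will be made to ensure the patient continues to be followed-up". Section 8.5.5 asks for follow-up of all patients over the full study, including those whose treatment is discontinued or changed. Where visits have stopped but consent stands, it asks for vital status at least six-monthly to Week 132. Section 14.3 keeps a patient who is given alternative treatment in the trial for follow-up and analysis.

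**The concern.** Stopping a trial regimen and leaving the trial are different instructions to a site. The first changes the drugs. The second, taken at its word, ends visits and data collection. Section 9.1 uses both within one paragraph for the same patients, and nothing in the documents defines the second as meaning the first.

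The data at stake are safety and survival data. Section 1.1.6 gives monitoring of safety, particularly deaths, as the main purpose of Stage 2 follow-up beyond Week 76. Section 2.2.1 answers the mortality imbalance in the earlier bedaquiline trial with a commitment to follow all participants to 132 weeks. A patient who took at least one dose stays in the safety population whatever happens next. Ending follow-up early would leave that patient in the denominator with an incomplete record.

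**Working it through.** No figure in the plan is in dispute, so the check is mainly a comparison of the text.

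**Step 1: the instruction in each place.**

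| Place (Protocol) | Trigger | Action |
|---|---|---|
| 5.5.1 | XDR-TB on phenotypic DST, pre-treatment samples | stop trial treatment |
| 8.7 | confirmed XDR-TB, baseline samples | stop trial treatment |
| 9.1, first XDR-TB sentence | resistance to both classes on phenotypic DST | stop trial treatment |
| 9.1, last XDR-TB sentence | central laboratory confirms XDR-TB | leave the trial |

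Three agree and one differs.

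**Step 2: which follow-up rule applies.** Confirmed resistance to both classes is item 8 on the list in 9.1 of reasons to discontinue or modify treatment. The follow-up requirement at the opening of 9.1 therefore covers these patients directly. Sections 8.5.5 and 14.3 cover them as patients whose treatment was stopped or changed. Section 9.4 allows early stopping of follow-up when a patient explicitly declines to give further data. It does not mention XDR-TB, so it supports the point only by implication. Section 5.5.2 states that patients found to be rifampicin-sensitive are followed on the trial schedule. Section 5.5.1 has no equivalent statement for XDR-TB, which leaves room for a literal reading of 9.1.

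**Step 3: which analyses are touched.**

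- *Primary analysis.* Protocol 11.1 and SAP 4.3 exclude XDR-TB in isolates taken before randomisation from mITT, and SAP 4.4 builds PP from mITT. The wording of 9.1 does not reach these patients' contribution, because they make none.
- *Sensitivity analyses K (ITT) and L (safety population), SAP 6.4.* These patients are included. They would normally be unfavourable either way, through a restart on a different MDR-TB regimen (SAP 3.2, criterion 1) or a missing Week 76 culture (criterion 10).
- *Grade 3 or greater events, SAP 7.2.3.* This is a difference in proportions over the whole study period in the safety population. SAP 7.2.3 does not say how shortened follow-up is handled. I assume that a patient with no recorded event counts as event-free.
- *Mortality, SAP 7.2.2.* Survivors are censored at their final visit, so an early end of follow-up means early censoring, and a later death could be missed.

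**Step 4: size per patient.** Take 200 per arm (Protocol 11.4.1). One patient wrongly counted as event-free lowers that arm's grade 3+ proportion by 1/200 = 0.005, or 0.5 points. Not every removed patient is misclassified. Assume the Stage 1 Regimen B rate of 48.2% (Protocol 2.1.1) and, as an extreme, that every event falls after removal. The average shift per removed patient is then 0.482 × 0.5 = 0.24 points. The documents give no number of patients by which to multiply this. Line-probe resistance to either class is an exclusion (5.2), which keeps the number down. Patients with inconclusive second-line results may be enrolled (5.4.2), so cases can occur.

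**The case against.** The strongest reply is that context settles the meaning. The sentence stands in a section on discontinuing the allocated regimen, directly after one about remaining on trial medication, so the natural contrast is on or off trial drugs. This is probably what was intended. It does not remove the defect: the sentence is an operative instruction, it uses a different and stronger phrase than its neighbour, and other sections contradict it as written.

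Safeguards also stand in the way of harm. "Any change or discontinuation of treatment should be discussed with the STREAM central clinical team before a decision is made", except in an emergency. Under 8.5.4 the loss-to-follow-up "designation cannot be made for any patient until after" the scheduled Week 132 visit. The six-monthly vital-status checks in 8.5.5 apply unless consent is withdrawn. Section 13 ends adverse event collection at completion of follow-up or when the participant withdraws, and does not name removal by a clinician. All of this stands. Data would be lost only if a site treated removal as the end of visits and nobody corrected it.

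Timing limits the benefit too. The protocol footer is dated 15 December 2020, and the last patient's Week 96 falls at about the end of November 2021. That places the last randomisation in late January 2020 and that patient near Week 46 at the footer date, past the planned 40 weeks of treatment. Even so, 132 − 46 = 86 weeks of that patient's safety follow-up remained.

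A reader might infer that the 9.1 sentence, which has no baseline limit, also orders removal for XDR-TB acquired on treatment. The documents do not support building on that. The paragraph in 9.1 refers to 5.5.1, which concerns pre-treatment samples, and 8.7 says that reference-laboratory resistance results are not routinely returned to sites.

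**Conclusion.** The inconsistency is real and minor, at the lowest level of severity. One sentence of 9.1 contradicts 5.5.1, 8.7 and its own paragraph on what happens to the patient. If followed literally, it also contradicts the follow-up rules in the opening of 9.1, 8.5.5 and 14.3.

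The consequence is confined to the safety and mortality analyses, for a probably small number of patients that the documents do not let one estimate. Each could move an arm's grade 3+ proportion by at most 0.5 points. This assumes 200 per arm and that a patient without a recorded event counts as event-free. The effect on the primary mITT and PP result is negligible.

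A reader might infer that the non-inferiority conclusion, its power or the mortality comparison is threatened. Nothing in the documents supports that: the affected baseline cases are outside both primary populations, and no count of cases is given. Nor should 9.4 be read as an express ban on removal by a clinician, since it addresses only patients who refuse further data.

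**What to change.** In Protocol 9.1, replace the instruction to remove the patient from the trial with: *withdrawn from trial treatment, with follow-up, adverse event and vital-status collection continuing to Week 132 under Section 8.5.5*.

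The cost is one phrase at the next amendment. No visit, test or form is added, because 8.5.5 already provides for following patients who stop treatment. The SAP needs no change.
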